7.3 XSTAT safety (Objective 5)

Although XSTAT[®] is thought to be a low-risk device, we will nevertheless obtain formal data on its safety profile, which will include the following:

- a) Number of patients suffering allergic reactions or anaphylaxis
- b) Number of patients developing wound infections
- c) Number of patients developing tissue damage thought to be related to the insertion of the device or deployment of the sponges
- d) Number of patients suffering embolization of the sponges
- e) Number of patients who suffer inadvertent retention of sponges (beyond first operation)
- f) Number of patients in whom no vascular injury is identified

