			0	No	
49	incl_jctl_injury	Penetrating junctional injury (groin or axilla)	rad	lio (Matrix)	
			1	Yes	
			0	No	
50	excl_prisoner	Section Header: Exclusion Criteria Present: To be eligible, all questions must be answered "No"	rad	lio (Matrix)	
		Prisoner, defined as those directly admitted from a correctional facility	0	No	
51	excl_age	Children under the age of 18 years or under 50kg if age	rad	lio (Matrix)	
		unknown	1	Yes	
			0	No	
52	excl_pregnancy	Known pregnancy	rad	lio (Matrix)	
			1	Yes	
1			0	No	

84	inj_named_vein_1 Show the field ONLY if: ([surg_proc_wound(1)] = '1' or ([num_wounds] = '1' and [ope ration_junction_site] = '1')) an d [current-instance] = 1	Injury to named veln?	radio (Matrix) 1 Yes 0 No
85	inj_unnamed_vessel_1 Show the field ONLY if: ([surg_proc_wound(1)] = '1' or ([num_wounds] = '1' and [ope ration_junction_site] = '1')) an d [current-instance] = 1	Injury to un-named vessel?	radio (Matrix) 1 Yes 0 No
86	inj_tissue_bleed_1 Show the field ONLY If: ([surg_proc_wound(1)] = '1' or ([num_wounds] = '1' and [ope ration_junction_site] = '1')) an d [current-instance] = 1	Tissue bleeding?	radio (Matrix) 1 Yes 0 No
87	inj_pleural_violation_1 Show the field ONLY if: ([wound_1_loc] = '1' and ([sur g_proc_wound(1]] = '1' or ([nu m_wounds] = '1' and [operati on_junction_site] = '1'))) and [current-instance] = 1	Pleural violation?	radio (Matrix) 1 Yes 0 No
88	inj_peritoneal_violation_1 Show the field ONLY if: ([wound_1_loc] = '2' and ([sur g_proc_wound(1)] = '1' or ([nu m_wounds] = '1' and [operati on_junction_site] = '1'])) and [current-instance] = 1	Peritoneal violation?	radio (Matrix) 1 Yes 0 No
89	op_arterial_ligation_1 Show the field ONLY if: [surg_proc_wound(1)] = '1' or [(num_wounds] = '1' and [ope ration_junction_site] = '1')	Section Header: Please describe the operative treatment on the wound to the [wound_tside]. [wound_t_orientation] [wound_t_loc]: Ligation of arterial injury	radio (Matrix) 1 Yes 0 No
90	op_venous_ligation_1 Show the field ONLY if: [surg_proc_wound(1)] = '1' or [num_wounds] = '1' and [ope ration_junction_site] = '1')	Ligation of venous injury	radio (Matrix) 1 Yes 0 No
91	op_arterial_repair_1 Show the field ONLY if: [surg_proc_wound(1)] = '1' or ([num_wounds] = '1' and [ope ration_junction_site] = '1')	Patch angioplasty, interposition grafting, or direct repair of arterial injury	radio (Matrix) 1 Yes 0 No

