92	op_venous_repair_1 Show the field ONLY if: [surg_proc_wound(1)] = '1' or ([num_wounds] = '1' and [ope ration_junction_site] = '1')	Patch angioplasty, interposition grafting, or direct repair of venous injury	radio (Matrix) 1 Yes 0 No
93	op_other_details Show the field ONLY if: [surg_proc_wound(1)] = '1' or [[num_wounds] = '1' and [ope ration_junction_site] = '1')	Other operative treatment/additional details:	notes

94	sponges_removed_dt_tm_1 Show the field ONLY If: [randomized_ym] = '1' and [xst _proc_wound(1)] = '1' or ([nu m_wounds] = '1' and [operati on_junction_site] = '1') and [x stat_used_wound_1] = '1'	Section Header: Please describe the experience removing the XSMT sponges from the wound to the (wound, I_side), (wound, I_orientation) (wound, I_olc): What was the date and time at which the sponges were finally removed (or when decision was made that they could not be removed? (M-D-Y H:M)	text (datetime_mdy)	
95	ease_sponge_remove_1 Show the field ONLY If: [randomized_ym] = '1' and [xst a_tatempted] = '1' and [Surg _proc_wound(1)] = '1' or ([nu m_wounds] = '1' and [operati on_junction_site] = '1') and [x stat_used_wound_1] = '1'	Please describe the ease of sponge removal	radio 1 Failed to remove all sponges 2 Reasonably easy to remove all sponges 3 Sponges easily removed	
96	time_sponge_removal_1 Show the field ONLY if: [randomized_ym] = '1' and [xst _tatempted] = '1' and [surg _proc_wound(1)] = '1' or ([nu m_wounds] = '1' and [operati on_junction_site] = '1') and [x stat_used_wound_1] = '1'	Please estimate the time required to remove the sponges	radio 1 31 minutes or longer 2 Between 5 and 30 minutes 3 Less than 5 minutes	
97	Imaging_sponge_removal_1 Show the field ONLY If: [randomized_yn] = '1' and [xst at_attempted] = '1' and [surg _proc_wound(1)] = '1' or ([nu m_wounds] = '1' and [operation on_junction_site] = '1']) and [x stat_used_wound_1] = '1'	Please describe what intraoperative imaging was used to ensure removal of the sponges	radio 1 Imaging not used due to patient's condition 2 Imaging not used, as not available 3 Imaging not used, as deemed unnecessary 4 Imaging used	
98	Imaging_outcome_1 Show the field ONLY if: [randomized_yn] = '1' and [ixagi ng_sponge_removal_1] = '4' and ([surg_proc_wound(1])] = '1' or ([num_wounds] = '1' an d [operation_junction_site] = '1') and [xstat_used_wound_ 1] = '1'	Describe the outcome	radio 1 Additional sponges were seen on imaging 2 No additional sponges were seen on imaging	

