99	xstat_satisfaction_1 Show the field ONLY if: [randomized_ym] = '1' and [xst at_attempted] = '1' and (surg _proc_wound(1)] = '1' or ([nu m_wounds] = '1' and [operati on_junction_site] = '1'] and [x stat_used_wound_1] = '1'	Please describe your overall satisfaction with the XSTAT device	radio 1 Dissatisfied 2 Neither satisfied nor dissatisfied 3 Satisfied	
100	inj_named_artery_2 Show the field ONLY if: [surg_proc_wound(2)] = '1'	Section Header: Please describe the findings for the wound to the [wound_2_side], [wound_2_orientation] [wound_2_loc]: Injury to named artery?	radio (Matrix) 1 Yes 0 No	
101	inj_named_vein_2 Show the field ONLY if: [surg_proc_wound(2)] = '1'	Injury to named vein?	radio (Matrix) 1 Yes 0 No	
102	inj_unnamed_vessel_2 Show the field ONLY if: [surg_proc_wound(2)] = '1'	Injury to un-named vessel?	radio (Matrix) 1 Yes 0 No	

103	inj_tissue_bleed_2 Show the field ONLY if: [surg_proc_wound(2)] = '1'	Tissue bleeding?	radio (Matrix) 1 Yes 0 No
104	inj_pleural_violation_2 Show the field ONLY if: [surg_proc_wound(2)] = '1' an d [wound,2_loc] = '1'	Pleural violation?	radio (Matrix) 1 Yes 0 No
105	inj_preitoneal_violation_2 Show the field ONLY if: [surg_proc_wound(2)] = '1' an d [wound_2_loc] = '2'	Peritoneal violation?	radio (Matrix) 1 Yes 0 No
106	op_arterial_ligation_2 Show the field ONLY If: [surg_proc_wound(2)] = '1'	Section Header: Please describe the operative treatment on the wound to the [wound_2_side], [wound_2_orientation] [wound_2_loc]: Ligation of arterial injury	radio (Matrix) 1 Yes 0 No
107	op_venous_ligation_2 Show the field ONLY if: [surg_proc_wound(2)] = '1'	Ligation of venous injury	radio (Matrix) 1 Yes 0 No
108	op_arterial_repair_2 Show the field ONLY if: [surg_proc_wound(2)] = '1'	Patch angioplasty, interposition, grafting, or direct repair of arterial injury	radio (Matrix) 1 Yes 0 No
109	op_venous_repair_2 Show the field ONLY if: [surg_proc_wound(2)] = '1'	Patch angioplasty, interposition, grafting, or direct repair of venous injury	radio (Matrix) 1 Yes 0 No

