110	sponges_removed_dt_tm_2 Show the field ONLY if: [randomized_yn] = '1' and [xst at_attempted] = '1' and [suta proc_wound(2]] = '1' and [xsta t_used_wound_2] = '1'	Section Header: Please describe the experience removing the XSIAT sponges from the wound to the [wound,2,ide], [wound,2, orientation] [wound,2,loc]: What was the date and time at which the sponges were finally removed (or when decision was made that they could not be removed? (M-D-Y H:M)	text (datetime_mdy)
111	ease_sponge_remove_2 Show the field ONLY if: [randomized_yn] = '1' and [xst at_attempted] = '1' and [surg_ proc_wound[2]] = '1' and [xsta t_used_wound_2] = '1'	Please describe the ease of sponge removal	radio 1 Failed to remove all sponges 2 Reasonably easy to remove all sponges 3 Sponges easily removed
112	time_sponge_removal_2 Show the field ONLY if: [randomized_yn] = '1' and [xst at_attempted] = '1' and [surg_ proc_wound[2]] = '1' and [xsta t_used_wound_2] = '1'	Please estimate the time required to remove the sponges	radio 1 31 minutes or longer 2 Between 5 and 30 minutes 3 Less than 5 minutes
113	imaging_sponge_removal_2 Show the field ONLY if: [randomized_yn] = '1' and [xst at_attempted] = '1' and [surg_ proc_wound(2]] = '1' and [xsta t_used_wound_2] = '1'	Please describe what intraoperative imaging was used to ensure removal of the sponges	radio 1 Imaging not used due to patient's condition 2 Imaging not used, as not available 3 Imaging not used, as deemed unnecessary 4 Imaging used
114	Imaging_outcome_2 Show the field ONLY if: [randomized_yn] = '1' and [sst at_attempted] = '1' and [srt proc_wound[2] = '1' and [ima ging_sponge_removal_2] = '4' and [ixstat_used_wound_2] = '1'	Describe the outcome	radio 1 Additional sponges were seen on imaging 2 No additional sponges were seen on imaging

115	xstat_satisfaction_2 Show the field ONLY if:	Please describe your overall satisfaction with the XSTAT device	radio 1 Dissatisfied
	[randomized_yn] = '1' and [xst at attempted] = '1' and fourg		2 Neither satisfied nor dissatisfied
	proc_wound(2)] = '1' and [xsta t_used_wound_2] = '1'		3 Satisfied
116	form_7_operative_treatment_	Section Header: Form Status	dropdown
	complete	Complete?	0 Incomplete
			1 Unverified
			2 Complete
Instr	rument: Form 8: Blood/Blo	od Product Transfusion Record (form_8_bloodblood_pro	duct_transfusion_record)
117	header_f8		descriptive
118	red_cell_units	Red cell concentrate (units)	text (integer) Field Annotation: @DEFAULT="0"

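### Form 7 opens the printed wound-1 findings fields (84-88) only in the first operation record, unlike the wound-1 treatment fields and the wound-2 findings

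*Protocol*

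**What the plan says.** The fields at issue sit in the codebook's operative treatment instrument ("form_7_operative_treatment"). The display rules use an instance variable, which implies that the form repeats, with one record per operation.

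- **Wound-1 findings, fields 84-88.** Each requires that wound 1 was operated on and, in addition, "current-instance] = 1". Field 85, for example, is "Injury to un-named vessel". Fields 87 and 88 also depend on wound location (axilla for pleural, groin for peritoneal violation).
- **Wound-1 treatment and notes, fields 89-93.** These run from "Ligation of arterial injury" (field 89) to "Patch angioplasty, interposition grafting, or direct repair of venous injury" (field 92) and a free-text field (93). They require only that wound 1 was operated on. The rule for field 91 begins "op_arterial_repair_1 Show the field ONLY if: [surg_proc_wound(1" and contains no instance condition.
- **Wound-2 findings, fields 100-105.** They require only that wound 2 was operated on, plus location for the two cavity items. The rule for field 101 begins "inj_named_vein_2 Show the field ONLY if: [surg_proc_wound(2" and also has no instance condition.

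Section 7.3(f) lists as a safety outcome the "Number of patients in whom no vascular injury is identified". The protocol does not say which codebook fields feed that count.

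**The concern.** The same information is collected under different rules for the two wounds. Within wound 1, what was done can be recorded at every operation, but what was found can be recorded only in record 1. A later record can therefore show a vessel repair in wound 1 and have no field for the injury that was repaired.

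Two uses of the data are at stake. Section 7.3(f) asks in how many patients no vascular injury was found, and the vein and un-named-vessel items are natural structured sources for it. Pleural and peritoneal violation bear on the risk described in section 13.2, that sponges enter a body cavity. A value that the form never asked for cannot be recovered by an analysis rule written later, so this is a matter for the form and not only for an analysis plan.

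**Working it through.** The protocol gives no figure to reproduce here. The check is to evaluate the printed display rules for first and later operation records.

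| Operation record | Wound 1 operated on? | Wound-1 findings (84-88)* | Wound-1 treatment and notes (89-93) |
|---|---|---|---|
| First | yes | open | open |
| First | no | closed | closed |
| Second or later | yes | **closed** | open |
| Second or later | no | closed | closed |

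*Fields 87 and 88 also need the matching wound location.

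The wound-2 findings open in any record in which wound 2 was operated on, whether first or later (again subject to location for the cavity items).

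Two routes lead to a gap for wound 1.

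1. *Record 1 does not cover wound 1* (for example wound 2 only, or another body site), and wound 1 is explored in record 2. At record 1 the wound condition fails, and at record 2 the instance condition fails. Fields 84-88 never open for that patient and stay missing.
2. *Record 1 covers wound 1, but a finding is first made at re-exploration.* Fields 84-88 were open at record 1 and may correctly hold No as of that operation. Record 2 offers no field for the new finding, so the No stands unless someone goes back and changes record 1.

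Later operations are foreseen: sections 7.3(e) and 8.4.7(e) count sponges retained past the first operation.

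What the other fields still capture in a later record:

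- artery or vein ligated or repaired: yes, fields 89-92;
- vessel injured but neither ligated nor repaired: free text only (field 93 or Form 14);
- tissue bleeding: free text only;
- pleural or peritoneal violation: free text, or Form 12 if it is reported there as an adverse device effect because sponges entered the cavity (section 14.3.2).

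Size of one misclassified patient, with the maximum enrolment of 50 from section 9:

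- all enrolled: 1/50 = 2 percentage points;
- XSTAT arm, assuming 1:1 allocation: 50/2 = 25, and 1/25 = 4 points;
- if the XSTAT arm were smaller: 1/20 = 5 points, 1/10 = 10 points.

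The protocol gives no basis for the number of patients who would follow either route, so no expected total is computed.

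**The case against.** Four stronger readings are tempting, and the protocol does not support them.

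- *That a late-found injury cannot be entered at all.* It can. Ligation or repair goes into fields 89-92 at any operation on wound 1, field 93 and Form 14 take free text, and nothing printed prevents correction of record 1.
- *That a blank will be read as no injury.* The items are coded 1 for Yes and 0 for No, so a field that never opened is missing, not 0. No rule in the protocol turns missing into No. Variable definitions are assigned to a procedures manual (section 15.1.2), and the derivation may sit in an analysis plan.
- *That the non-therapeutic exploration count, which section 5.2 treats as a key outcome, is inflated.* Section 5.2 frames it by whether the injury needed operative treatment, and section 14.3.2 words the related event by absence of a vessel needing ligation or repair. On that reading the treatment fields decide, and they open at every operation on wound 1.
- *That the error amounts to many percentage points.* That needs an assumed frequency for which the protocol has no source. It also needs every such patient to have an untreated vessel injury, no free-text entry and no correction of record 1.

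It can also be said that asking for findings once and treatment each time is a sensible way to avoid duplicates. That does not explain the design: the same rule would then apply to wound 2, and it would be tied to the first exploration of the wound, not to the record number.

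Section 8.2 provides logic checks, a 20% audit and resolution of suspect entries before lock. These may catch some cases, but a field that never opened is not in itself a suspect entry.

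One limit stands in full. Fields 53-83 are absent from the text available here, including the start of Form 7 and probably the wound-1 named-artery item. Whether that item carries the same condition cannot be checked. Nor can it be seen whether record 1 means the first operation of any kind or the first at a junctional site. If the latter, the other-site route disappears, but the wound-2-only and re-exploration routes remain.

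**Conclusion.** The inconsistency is real and can be read directly from the codebook. It leaves a limited gap in data capture, of minor severity. The exposed items are wound-1 vessels neither ligated nor repaired, tissue bleeding, and cavity violation first seen in a later record. Outcome 7.3(f) is at risk only if it is derived from the findings fields without the treatment fields.

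Each patient misclassified would move that outcome by 2 points of 50, or 4 points of 25 under the 1:1 assumption. How many there would be is unknown and may be none. The conclusion assumes that Form 7 holds one record per operation, as the instance variable implies, and makes no claim about the unseen fields.

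**What to change.** Remove the instance condition from fields 84-88, and from the wound-1 artery item if it has one, so that wound 1 follows the same display rule as wound 2. State, in the protocol or the analysis plan, that 7.3(f) is counted over all operation records, using the findings fields and the ligation and repair fields together, so that a recorded ligation or repair counts as a vascular injury.

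The cost is one edit to the database's branching logic and a sentence of definition. The only downside is that the findings matrix appears again at re-operations, as it already does for wound 2.

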7.2.1 Prehospital setting (Objective 3)

Many civilian penetrating injuries are caused by low energy transfer firearms (typically handguns). The resulting wounds can be small, which may make insertion of the XSTAT[®] device difficult. We will evaluate the usability of the device in the prehospital setting, by investigating the following:

- a) Ease of insertion
- b) Ease of deployment
- c) Overall satisfaction with the device

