7.2.2 Operating room (Objective 4)

Use of the XSTAT device commits the patient and medical team to operative exploration of the wound, and retrieval of the sponges. We will evaluate surgeons' views on the device, by collecting data on the following:

- a) The ease of sponge removal
- b) The time required to remove the sponges

- c) The use of x-rays/image intensifiers to ensure complete removal of the sponges
- d) Overall satisfaction with the device

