8.3 Patients entered into pilot trial: Prehospital data collection

The PhoXSTAT trial requires the collection of a minimal amount of prehospital data – primarily relating to the usability and safety of the device. Each trial intervention pack contains a tracking label, which must be attached to the patient, using the cable tie supplied. The tracking label contains a mini-questionnaire. If the patient was allocated to treatment with Xstat, the following details must be completed:

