8.4.1 Physiological parameters

The following measurements are collected on admission:

- a) Systolic, diastolic, and mean blood pressure
- b) Heart rate
- c) Shock index
- 8.4.2 Usability

The ease of sponge removal

- a) Unable to remove all sponges
- b) Reasonably easy to remove all sponges
- c) Sponges easily removed

The time required to remove the sponges

- a) 1 hour or longer
- b) Between 5 and 59 minutes
- c) Less than 5 minutes

The use of x-rays/image intensifiers to ensure complete removal of the sponges

- a) Imaging not used due to patient's clinical condition
- b) Imaging not used as not available
- c) Imaging deemed unnecessary
- d) Imaging used

Outcome of imaging:

- a) Additional sponges seen on imaging
- b) No additional sponges seen on imaging

Overall satisfaction with the device

- a) Dissatisfied
- b) Neither satisfied nor dissatisfied
- c) Satisfied

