18. APPENDICES

Appendix 1: Sample tracking label

The tracking labels are found inside the study packs. They are printed on stiff, waterproof card, are hole-punched, and be supplied with a tie. The label should be completed as directed, and then attached to the patient's wrist or ankle. Labels are specific to trial sites.

PhoXSTAT	Prehospital XSTAT Trial	Kit Number:	
FIRST WOUND TR	EATED	SECOND WOUND	TREATED (IF APPLICABLE)
R	How many devices used on this wound? Only one XSTAT used on this wound Both XSTATs used on this wound	2	How many devices used on this wound?
	Ease of insertion of device into wound: Unable to insert Reasonably easy to use Easily inserted		Ease of insertion of device into wound: Unable to insert Reasonably easy to use Easily inserted
	Ease of deployment of sponges: Unable to deploy sponges Reasonably easy to deploy sponges Easily deployed		Ease of deployment of sponges: Unable to deploy sponges Reasonably easy to deploy sponges Easily deployed
Mark Location	Time device used:	Mark Location	Time device used:
Date:		Vehicle ID:	

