Appendix 2: Data Dictionary Codebook

The University of Alabama Ophthalmology Services Foundation

PhoXSTAT

🛄 Codebook 🔻

📖 Data Dictionary Codebook

04/19/2019 1:29pm

r

	 Conapse all instruments 			
	Variable / Field Name	Field Label Field Note	Field Attributes (Field Type, Validation, Choices, Calculations, etc.)	
Instr	strument: Form 5: Randomized to XSTAT (form_5_randomized_to_vstat)			
1	kit_number	Kit label #	text, Identifier	
2	vehicle_id	Vehicle ID #	text	
3	header_f6		descriptive	
4	num_wounds	Section Header: Describe the wounds treated with XSTAT:	radio	
	Show the field ONLY if: [vehicle_id] <> ""	How many wounds were treated with XSTAT?	1 1 2 2	
5	wound_1_loc	Where was the anatomical location of wound #1?	radio	
	Show the field ONLY if: [num_wounds] = '1' or [num_ wounds] = '2'		1 Axilla 2 Groin	
6	wound_1_side	On which side of the body was the wound #1?	radio	
	Show the field ONLY if:		1 Left	
	[num_wounds] = '1' or [num_ wounds] = '2'		2 Right	
7	wound_1_orientation	What was the anatomical orientation of wound #1 (Choose all	checkbox	
	Show the field ONLY if:	that apply)?	1 wound_1_orientation1 Anterior	
	[num_wounds] = '1' or [num_		2 wound_1_orientation2 Posterior	
	wounds] = '2'		3 wound_1_orientation3 Medial	
			4 wound_1_orientation4 Lateral	
8	wound_2_loc	Where was the anatomical location of wound #2?	radio	
	Show the field ONLY if:		1 Axilla	
	[num_wounds] = '2'		2 Groin	
9	wound_2_side	On which side of the body was wound #2?	radio	
	Show the field ONLY if:		1 Left	
	[num_wounds] = '2'		2 Right	
10	wound_2_orientation	What was the anatomical orientation of wound #2 (Choose all	checkbox	
	Show the field ONLY if:	that apply)?	1 wound_2_orientation1 Anterior	
	[num_wounds] = '2'		2 wound_2_orientation2 Posterior	
			3 wound_2_orientation3 Medial	
			4 wound_2_orientation4 Lateral	
11	kit_opened_yn	Section Header: Describe the use of the study protocol:	yesno, Required	
	Show the field ONLY if:	Was kit opened?	1 Yes	
	[num_wounds] = '1' or [num_ wounds] = '2'		0 No	
12	randomized_yn	Was the patient randomized to treatment with XSTAT syringe?	yesno, Required	
	Show the field ONLY if:		1 Yes	
	[kit_opened_yn] = '1'		0 No	

13	xstat_attempted	Was treatment with XSTAT attempted?	yesno, Required		
	Show the field ONLY if: [randomized_yn] = '1'		1 Yes 0 No		
14	violation_reason	Please state reason(s) for protocol violation	notes		
	Show the field ONLY if: [xstat_attempted] = '0' and [r andomized_yn] = '1'				

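### Section 8.4.2 and Form 7 cut sponge-removal time at different points, and the sample tracking label and Form 5 lack the crew satisfaction item that Section 8.3.1 requires

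*Protocol*

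**What the plan says.** **Removal time.** Section 7.2.2 lists "The time required to remove the sponges" as an operating-room usability outcome under Objective 4. Section 8.4.2 gives it three classes: under 5 minutes, "Between 5 and 59 minutes", and an hour or more. In the Appendix 2 codebook, Form 7 asks the surgeon to estimate the time in field 96 (wound 1) and field 112 (wound 2). Both fields offer "31 minutes or longer 2 Between 5 and 30 minutes 3 Less than 5 minutes".

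**Crew satisfaction.** Section 7.2.1 lists "Overall satisfaction with the device" as a prehospital usability outcome under Objective 3. Section 8.3 places a short questionnaire on the tracking label and says: "If the patient was allocated to treatment with Xstat, the following details must be completed". Section 8.3.1 then lists ease of insertion, ease of deployment and overall satisfaction, each with three levels. On the Appendix 1 sample label the last rated item is ease of deployment, with the options "Unable to deploy sponges Reasonably easy to deploy sponges Easily deployed"; only location, time, date and identifiers remain. The codebook form that receives the label data is "Form 5: Randomized to XSTAT", fields 1-24. It has no satisfaction item.

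**The concern.** Usability is one of the trial's three groups of objectives, and Section 10.2 undertakes to report it. The class boundaries and the list of questions are fixed when the forms are issued. An analysis plan cannot later split a pooled tick or recover a rating that nobody was asked for. Used as shown, Form 7 would pool removals of 31-59 minutes with those of an hour or more. The label would not ask crews for one of the three prehospital outcomes that the protocol names.

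**Working it through.** No power or sample size figure is involved. The check sets the two definitions and the item lists side by side.

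**Removal time**

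| Actual removal time | Section 8.4.2 class | Form 7 tick |
|---|---|---|
| under 5 min | fastest | fastest |
| 5-30 min | middle | middle |
| 31-59 min | middle | slowest |
| 60 min or more | slowest | slowest |

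Let *a*, *b* and *c* be the numbers of Form 7 ticks in the fastest, middle and slowest boxes, and let *x* be the unknown number among the *c* that took 31-59 minutes (0 ≤ *x* ≤ *c*). In the classes of Section 8.4.2:

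- fastest = *a*, exact;
- middle = *b* + *x*, between *b* and *b* + *c*;
- slowest = *c* − *x*, between 0 and *c*.

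If *c* = 0, all three counts are recovered exactly. If *c* > 0, the middle and slowest counts are each uncertain by *c*, although their sum *b* + *c* is known.

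Could the duration be rebuilt from time stamps? Fields 94 and 110 ask "What was the date and time at which the sponges were finally removed" (or when removal was abandoned), which marks the end. Fields 18 and 21 record insertion. The difference between the two is how long the sponges stayed in, including transport and the wait for surgery, and not the time taken to remove them. No start-of-removal time appears in the fields shown. Fields 53-83, which include the opening of Form 7, are not in the text available, so one there cannot be excluded.

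**Crew satisfaction**

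- Section 8.3.1 requires 3 rated usability items: insertion, deployment and satisfaction.
- The sample label carries 2 of the 3 per wound. Satisfaction is missing.
- Form 5 runs unbroken from field 1 to field 24. Its label block is fields 15-23, which is 23 − 15 + 1 = 9 fields: number of devices (1), use on each wound (2), time of insertion (2), ease of insertion (2) and ease of deployment (2). None asks for satisfaction.
- Form 7 fields 99 and 115 do ask for satisfaction, but they sit in the operative form. They open only when that wound was operated on and XSTAT was used on it. They match the separate surgeon outcome in Section 7.2.2 and do not record the crew's view.

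**Extent**

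Section 7.2.1 lists 3 outcomes and Section 7.2.2 lists 4, so 3 + 4 = 7. One of each is affected: 1 + 1 = 2 of 7.

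**The case against.** The best defence is that this is routine form reconciliation in a descriptive pilot. Section 7 says there is no primary outcome, and no decision threshold rests on either item. Appendix 1 is headed a sample, and Section 16.2.1 calls the Appendix 2 form a sample and says the forms will be tested and finalised. The codebook is dated April 2019, within the planning year. All of this is fair and limits the weight of the point. It does not remove the conflict, because Section 8.2 cites Appendix 2 as the case report forms and nothing in the text says which version governs. Form 5 also supports the label evidence, since it lacks the same item.

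Three stronger readings are tempting, and the document does not support them.

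- *The middle and slowest removal-time classes can never be counted.* Only one of the three ticks is ambiguous. If it is never used nothing is lost, and if it is used the counts remain bounded.
- *Crew satisfaction has no source anywhere in the case report form.* With fields 53-83 unseen, this cannot be asserted. The supportable claim concerns the label and Form 5. A field elsewhere would still leave unrepaired the label that Section 8.3 makes the crew's collection tool.
- *A safety outcome is lost, because the prehospital anaphylaxis entry of Section 8.3.2 is also missing from the label and Form 5.* Section 8.4.7, the reporting period in Section 14.2 and Form 12 still provide a route for it.

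Nor can the effect be stated as a share of patients from the anticipated maximum of 50. No allocation ratio is stated, removal is recorded per operated, XSTAT-treated wound, and the number of removals over 30 minutes is unknown.

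**Conclusion.** The point stands as two internal contradictions that should be corrected. First, the removal-time classes of Section 8.4.2 and of Form 7 fields 96 and 112 agree only for the fastest class, so any tick in Form 7's slowest box leaves the protocol's middle and slowest counts bounded rather than known. Second, the crew satisfaction item that Section 8.3.1 requires is absent from the sample label and from Form 5.

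Two of seven descriptive usability outcomes are affected. No hypothesis test, sample size or safety outcome changes. The conclusion assumes that the label and codebook as printed are the instruments to be used. Confidence is high for the cut-offs and for the gap in the label and Form 5. What the unseen fields 53-83 hold remains open.

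**What to change.** Use one set of removal-time cut-offs in Section 8.4.2 and in Form 7 fields 96 and 112. Alternatively, have those fields record estimated minutes and form the classes at analysis; this is a preference, and aligned cut-offs would be enough.

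Add an overall satisfaction item, with the three levels of Section 8.3.1, to the tracking label and to the label block of Form 5. An anaphylaxis tick box in the same places is an optional consistency edit with Section 8.3.2.

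The cost is a reprinted label, a few edited database fields and a short text alignment, ideally before enrolment starts. The downside is a slightly longer label for crews to complete.
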